The profile of the child in terms of their developmental status based on initial evaluation results and an individualised intervention plan (IIP) will be discussed by the therapist with parents. The therapist will coach parents in the context of clinic-based play activities and help parents identify contexts and activities at home where the parents could follow up on the program at home. Children and their parents will receive the standard program which consists of 16 clinic-based intervention sessions of 60 min each, separated into 3 intervention blocks, with breaks in between so that parents will have opportunities to practise at home. This arrangement also allows parents who had missed their scheduled sessions to have make-up sessions during the breaks. Intervention sessions empower and equip parents with skills and strategies to engage with their child at home. Since the program involves behavioural intervention and parent coaching, active participation of parent and child are key to each session. However, realistic challenges in terms of child/parent or therapist being unwell, or when the

parent has work related commitments, may require rescheduling or cancellation of some visits. These are not anticipated to have any adverse impact on the child's health or the study.

Intervention: Telerehab Program

The intervention will commence with 2 clinic-based intervention sessions of 60 min each to provide adequate opportunity to engage in relational family-centred practices, joint decision and planning of the IIP based on initial evaluations and explore effective strategies as foundation to the subsequent interactions and coaching through VC.

Setting: Prior to intervention sessions, the therapist and parent will discuss and identify a suitable and feasible location to place the devices of their choice that would provide clear unobstructed views of parent-child interactions and activities. For 16 sessions, the therapist and parent will log onto the MOHH VC portal for the VC call.

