Patients will be recruited for the program after obtaining a preliminary diagnosis of ASD from the developmental paediatrician. ADOS-2 will be administered to confirm the diagnosis and thus participation in the research study. We will not be advertising this study to the public.

Pilot

An initial pilot feasibility study with 6 children and families will be conducted at the start of the project to identify any practical issues or weaknesses in the program or protocol before full scale evaluation.

Sample Size Calculation

The randomized trial is designed as a non-inferiority study to compare the changes in MSEL between 2 interventions. We expect that the change in MSEL score for the subjects in the new intervention arm will be slightly better than that in the control arm by 1.5 units. Assuming the SD of changes in MSEL score is 15 units, with 5 units as the non-inferiority margin, based on a one-sided test with 80% power and 5% significance level, it is sufficient to recruit 132 subjects (66 in each arm). We decided to recruit 200 subjects in total (100 in each arm) after considering withdrawals and lost to follow up. The computation was performed using a proprietary software programmed in R.

Randomisation Process and Blinding

Computer-generated randomisation will be used to randomly assign the participants to one of the intervention groups. Block randomisation will be used to allocate the recruited subjects into one of the interventions. A randomisation list will be generated by the study statistician and envelopes will be prepared. Although the allocation of intervention will be concealed and the study team will not know in advance which subject will receive which intervention, the blinding will not be possible once the intervention is assigned. Assessors of the initial and final MSEL were not told of the intervention status of the patient to avoid bias in outcome assessment. Blinding of the parents is not possible in the context of this study. Phone calls will be made if necessary to confirm appointments and/or before commencing consultation over video conference in the Telerehab group. Parents in both study arms will be encouraged to spend 2h per week in quality interactions with their children.

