Protocol deviation is defined as any divergence from what was pre-planned and approved by the institutional review board. As the study is conducted as part of routine care and operations, there are practical constraints that may cause protocol deviations to occur. Rescheduling of appointments by the parents (e.g. due to work constraints, child's sickness, other events) or defaulting appointments is inevitable. Hence, for per-protocol analyses, we will only exclude participants with major protocol deviation, which will be defined as participants who do not complete 80% of the intended therapy sessions allocated for their study arm. This means that a control arm participant must attend at least 8 out of 10 clinic-based sessions. For the remaining 2 sessions, participants can either be attending it through video-conferencing (due to the COVID-19 pandemic) or miss the appointment.

Quantitative Outcomes

For the randomized trial, since the study is a non-inferiority study, statistical analysis will be carried out on a per-protocol basis. Subjects with any major protocol deviation as defined above will be excluded from the final analysis.

All demographic, clinical and cost characteristics will be analysed descriptively. Mean (SD) or median (range), whichever is more appropriate will be reported for numerical variables, while N (%) will be reported for categorical variables. 2-sample t-tests, or Mann-Whitney U tests will be used to compare the change of MSEL score between 2 arms. Mean difference and 95% CI will be estimated. If the lower boundary of the 95% CI is more than -5, non-inferiority will be declared. Changes in the quality of parent-child engagement, parental stress index score, and adaptive score will be compared by using either a 2-sample t-test, or a Mann-Whitney U test, whichever is more appropriate. Linear regression will be used to adjust for any covariates.

Cost-Effectiveness Analysis

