The expected duration of the HSDP project was 3 years, from 01 June 2018 to 31 May 2021. As of January 2021, the Principal Investigator (PI) of the study, [name] has decided to extend the study to fulfil the targeted recruitment number. The study is expected to end on 31 May 2023. See Table 4 for the updated evaluation time frame.

Table 4: Updated evaluation time frame as of June 2021

	Program Year	Year 1				Year 2				Year 3				Year 4				Year 5				Year 6		
	Quarter	Q1	Q2	Q3	Q4	Q1	Q2	Q3	Q4	Q1	Q2	Q3	Q4	Q1	Q2	Q3	Q4	Q1	Q2	Q3	Q4	Q1		
	('YY)	18	18	18	19	19	19	19	20	20	20	20	20	21	21	21	21	22	22	22	22	23	23	
	Month	Jun	Sep	Dec	Mar	Jun	Sep	Dec	Mar	Jun	Sep	Dec	Mar	Jun	Sep	Dec	Mar	Jun	Sep	Dec	Mar	May		
Phase	Activity																							
Program preparation	Manpower, training	X																						
Program development & stabilization	Adapt and finalise, conduct feasibility study		X																					
Implementation	Enrolment and data collection for Year 1			X	X																			
Implementation	Enrolment and data collection for Year 2					X	X	X	X															
Preliminary data analysis	Analysis of Year 1 data including Year 1 follow-up							X	X															
Implementation	Enrolment and data collection for Year 3									X	X	X	X											
Study-Progress Report	For MOH Grant Extension												X											
Implementation	Enrolment and data collection for Year 4													X	X	X	X							

MOH Bi-Annual report	Every March and Sep														X		X					
Implementation	Data collection for Year 5 (no more enrolment)																	X	X	X	X	
MOH Bi-Annual report	Every March and Sep																		X		X	
Final Analysis	Consolidation and analysis of final data																					X

Dissemination of Findings

We propose to disseminate results to three primary groups of internal and external stakeholders

Group	Aim	Timing of dissemination	Method
NUHS management	To make decisions about the program but also about the general policies related to “big data”	Ongoing	Briefing and research round presentations
HSDP management / MOH stakeholders		Periodic results per the HSDP contract.	Reports, briefing; at discretion of HSDP/MOH
Academics, researchers and clinicians	To support	After endline data collection	Publications, presentations, seminars

Quality Assurance and Ethics

Quality Review

To ensure quality for the evaluation, we will seek review of the final analysis and report by an independent senior faculty member affiliated with CHSPR.

Research Ethics

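### A pandemic switch to video can on its own exclude control children, but not telerehab children, from the only named analysis set, so the calendar mix of the arms may differ

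*Combined protocol and SAP*

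**What the plan says.** Protocol Deviation and Per-protocol Analysis defines a major deviation, for both arms, as "participants who do not complete 80% of the intended therapy sessions allocated for their study arm". It spells this out for the control arm only: "a control arm participant must attend at least 8 out of 10 clinic-based sessions". For the other two sessions it then adds: "participants can either be attending it through video-conferencing (due to the COVID-19 pandemic) or miss the appointment". No corresponding statement about mode of delivery is made for telerehab.

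Quantitative Outcomes puts the trial analysis on a per-protocol basis and drops children with a major deviation. Non-inferiority is declared if the lower limit of the 95% CI for the difference in MSEL change lies above -5. Regression adjustment is allowed, but no covariate is named. No intention-to-treat analysis is stated, nor any analysis that treats switched sessions as attended.

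On the planned sessions, Intervention: Standard Program describes a "standard program which consists of 16 clinic-based intervention sessions of 60 min each". For telerehab, "The intervention will commence with 2 clinic-based intervention sessions of 60 min each", followed by 16 video sessions. Table 1, Annex 1 and Annex 2 give the same totals: 16 for control, and 2 + 16 = 18 for telerehab.

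On timing, Randomisation Process and Blinding states: "Block randomisation will be used to allocate the recruited subjects into one of the interventions". The project began on 1 June 2018. Table 4 runs enrolment from the third quarter of Year 1 through the row "Enrolment and data collection for Year 4", and the extended study ends on 31 May 2023.

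**The concern.** Blocked allocation keeps the two arms close to balance as enrolment proceeds, so whatever changes over calendar time falls on both arms alike. The mode rule acts after randomisation, in one arm, and for a reason the protocol itself ties to the pandemic. A control child may attend every session and still be removed because too many were by video. A telerehab child treated in the same months, with the same clinic disruption, stays in.

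If enough control children are removed this way, children treated under restrictions make up a smaller share of the control mean than of the telerehab mean. Any effect of that period on development, parental stress or assessment would then be read partly as an effect of telerehab. This would enter the comparison with -5 and the comparisons of parental stress, adaptive behaviour and parent-child engagement. Because per-protocol is the only set named and calendar period is not a stated covariate, nothing in the plan would reveal or correct it.

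**Working it through.** **1. The plan's own figure.** Inputs from Sample Size Calculation: SD 15, margin 5, expected advantage 1.5, one-sided 5%, power 80%.

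n per arm = 2 × 15² × (1.645 + 0.842)² / (5 + 1.5)² = 450 × 6.18 / 42.25, about 65.8, rounded up to 66, or 132 in total. The stated size is reproduced.

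**2. Who can be excluded by a switch to video alone.** Take a control child who attends every session, with some moved to video:

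| Reading of the control rule | Clinic sessions needed | Switched sessions that exclude |
|---|---|---|
| 8 of 10, as written | 8 of 10 | 3 or more of 10 |
| 80% of the 16 planned | 0.8 × 16 = 12.8, so 13 | 4 or more of 16 |
| A count of 8, applied to 16 | 8 of 16 (50%) | 9 or more of 16 |

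The third reading conflicts with the 80% definition, but the text does not rule it out. On every reading some fully attending control children can be excluded; how many depends on the denominator.

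Telerehab: 80% of 18 is 14.4, so 15 sessions are needed. If both clinic sessions moved to video and neither were credited, the 16 video sessions alone give 16/18 = 88.9%. The switch does not exclude the child without missed sessions as well.

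**3. Effect on calendar mix.** Let p be the share of each arm treated under restrictions, and e the share of those control children who exceed the allowance. The restricted-period share is p in telerehab and p(1 - e)/(1 - pe) in the retained control arm. Multiply the difference by a period effect on MSEL change, here 5 points. The documents give none of p, e or the 5 points; all are assumptions.

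| p | e | Control share | Telerehab share | Difference | Shift at 5 points |
|---|---|---|---|---|---|
| 0.2 | 0.25 | 0.15/0.95 = 15.8% | 20% | 4.2 pp | 0.21 |
| 0.4 | 0.25 | 0.30/0.90 = 33.3% | 40% | 6.7 pp | 0.33 |
| 0.2 | 0.5 | 0.10/0.90 = 11.1% | 20% | 8.9 pp | 0.44 |
| 0.4 | 0.5 | 0.20/0.80 = 25.0% | 40% | 15.0 pp | 0.75 |
| 0.2 | 1 | 0% | 20% | 20.0 pp | 1.0 |
| 0.4 | 1 | 0% | 40% | 40.0 pp | 2.0 |

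For e from 0.5 to 1 the shift is 0.4 to 2.0 points, or 9% to 40% of the margin. At e = 0.25 it is 0.2 to 0.3 points. The sign may go either way.

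**4. Power.** With 100 per arm and only control children lost, power at one-sided 5% is 92.2% with no loss, 89.3% with 20 lost and 84.3% with 40 lost. At one-sided 2.5%, which a two-sided 95% CI implies, it is 86.5%, 82.4% and 75.6%. Unless losses are heavy, the main issue is selection and not power.

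**The case against.** A per-protocol set in a non-inferiority trial may reasonably exclude control children who received much of the experimental mode. Keeping them pulls the arms together and favours a finding of non-inferiority. That stands: the rule itself is defensible. What is missing is protection against its one-sided link to calendar time.

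The plan also has features that limit exclusion. Control families may take make-up sessions in the breaks between blocks, and Program Timeline moves a child on only when the previous phase is complete, so some children could wait for clinic sessions. This argues against values of e near 1. Program Timeline also accepts timing variation as a limitation to weigh at interpretation, but that is not an analysis remedy.

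The size rests entirely on assumption. The documents give no dates for restrictions and no count of switched sessions, and the 5-point effect equals the whole margin. This stands.

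A reader might infer that the per-protocol arms come from different calendar periods. The documents do not support that. Control children treated under restrictions stay in if their switched or missed sessions fall within the allowance, and children treated outside restrictions stay in both arms. Even with e = 1 the arms would share all other periods. Nor does the rule as a whole remove only control children: telerehab children who miss too many sessions are excluded under the same 80% definition. Only exclusion by mode switch alone is confined to controls.

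**Conclusion.** The concern holds in a limited form. A pandemic switch to video can by itself remove a control child, and cannot by itself remove a telerehab child, from the only analysis set named. The removal follows randomisation and depends on arm, so the calendar mix of the arms may differ, and no adjustment or sensitivity analysis is planned.

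The asymmetry follows from the text. The amount and direction of bias do not: the 0.4 to 2.0 points are an illustration under assumed p, e and period effect, and smaller e gives less. The cut-off of about 20% also depends on resolving the conflict between 8 of 10 and the 16 planned control sessions. The matter deserves a change to the analysis plan, but the documents do not show that the primary result is materially biased.

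**What to change.** 1. Reconcile the 8-of-10 wording with the 16 control sessions in Intervention: Standard Program, Table 1, Annex 1 and Annex 2, and state the threshold for each arm. Until then the set of excluded children is undefined.
2. Keep the mode rule for the per-protocol set if wanted. Include calendar period of randomisation, with cut-points fixed before outcomes are compared, as a covariate in the MSEL regression, and state that this regression supplies the interval compared with -5. Do not use overlap of treatment with restrictions: it arises after randomisation, and Program Timeline says block durations may differ by arm. Adjusting for overlap, or dropping overlapping children, could introduce new selection.
3. Add a sensitivity analysis that counts control video sessions as attended, or an as-randomised analysis. Period adjustment addresses calendar mix only; this also addresses differences between excluded and retained control children within a period.
4. Report exclusions by arm, reason and period.

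The cost is analysis-plan wording, one covariate and one extra table. Applying the rule already requires session mode, and the period covariate needs only the randomisation date. The downside is that the sensitivity analysis readmits control children partly treated by video, which can pull the arms together. It should be read beside the per-protocol result and not replace it.

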Midpoint IIP review: Therapists will review the child on the individualized intervention plan (IIP) developed after baseline assessment and plan for further intervention.

Final Reviews and Assessments: Visit 12 to 14

The final reviews and assessments will be conducted across three sessions, which can take place in any order depending on the participant's availability and therapist's schedule.

Final Review with Therapist: The child will be evaluated on the baseline assessment measures. Parents will also be given a parent satisfaction survey, cost survey and FEIQoL survey to complete. If parents are unable to complete the surveys during their clinic-based session, they will be sent the surveys through email or asked to answer the questions over a phone call. For children in the telerehab group, there will be a VC review in addition to the clinic-based assessment.

Nurse Assessment: The child will be evaluated on MSEL. The Parental Stress Index will be administered as part of this assessment.

Psychologist Assessment: VABS-III will be administered to the parent for this assessment.

Final Paediatrician review: Visit 15

[figure not shown]
This last paediatrician visit is for the paediatrician to share the reports on the evaluations, discuss progress and further needs of child and family.

Transfer to Early Intervention Programs

CDU provides interim therapy for children pending their enrolment into an EIPIC (or private early intervention service). Under normal circumstances, the child does not receive any intervention from EIPIC in the first 10 weeks on enrolment as the child is being assessed. In this transition period, the child continues to receive CDU intervention per standard clinical practice. As such, children in this study will continue to receive intervention for 10 weeks after EIPIC enrolment. Similarly, children who has been transferred to a private intervention service will continue to receive intervention per the study protocol as long as they have not started receiving intervention at the private service.

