Children also continue to remain as CDU patients under the care of their doctors until age 7, regardless of whether they have been enrolled to an EIPIC or private service. As such, study participants who have been transferred to an EIPIC will still be assessed per protocol for Midterm Progress Reviews and Final Reviews and Assessments. As far as possible, these assessments will be scheduled to coincide with their doctor's follow-up at the CDU as part of standard care.

Logic Model for Telerehab Program

Evaluation Framework

Literature Review

There is a dearth of published research on the use of telehealth in coaching for parents of children with autism spectrum disorders. A literature search found only two representative studies (Vismara et al, 2013 and Maedan et al, 2016) both from the United States and with small sample size.

One study followed eight families over a 12-week online video conference based intervention with three month follow up. Parents reported a better understanding of and appreciation for helping their children new skills, as well as increased confidence in addressing their child's needs and sharing information with other caretakers. The other described a similar Internet-Based Parent-Implemented Communication Strategies (i-PiCS) parental coaching program with 3 mother-child dyads and found positive changes in children's communication skills with the implementation of the strategies taught in coaching. As illustrated by the sample size <10 in each, neither previous study followed a rigorous RCT methodology but both studies highlighted the potential of telehealth as a feasible service-delivery option for parental coaching and called for further more robust studies of telehealth interventions with a greater diversity of participants.

Evaluation Questions

Effectiveness Trial

Primary Research Question: Is the tele-health intervention as effective as standard care in improving short and long-term outcomes for children and parents?

Process Evaluation

- How feasible and acceptable is the tele-health intervention?
- What features or conditions make the tele-health intervention more or less effective?
- What could be improved with acceptability, feasibility and scalability in mind?

Cost-Effectiveness

Is the tele-health intervention cost-effective (cost-saving) relative to standard care?

Indicators and Outcomes

Evaluation Question	Primary indicator required	Measurement & Reference	Expected change

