Parent-delivered therapy (home-based)				
Visit 9	Midpoint IIP Review with Therapist (clinic based)	60	Midpoint IIP Review with Therapist (clinic based)	60
3 rd block of intervention	Clinic-based intervention x 6	60 x 6	Video conference-based intervention (VCBI) x 2	45 x 2
	Parent-delivered therapy (home-based)			
Visit 10-11	Fifth Paediatrician visit Midpoint Review by paediatrician (clinic based or teleconsultation)			30
	
 • Child's profile, progress • Child and Family's needs • Appropriate recommendations and referrals (if needed) 			
	Review with Therapist (clinic based)			60
	
 • Foundational skills curriculum – Child's development profile • Joint Engagement Rating Inventory (JERI) • Cost Survey 			

4 th intervention block	Parent-delivered therapy (home-based)	Video conference-based intervention (VCBI) x 6	45 x 6
		Parent-delivered therapy (home-based)	
Visit 12-14	Final Review with Therapist (clinic based)		90
	
 • Foundational skills curriculum (FSC) assessment • Joint engagement rating inventory (JERI) • Family Early Intervention Quality of life survey (FEIQoL) • Cost Survey 		
	Additional Indicators to baseline:		
	
 • Parent Satisfaction Survey 		
	Final Nurse Assessment (clinic based)		120
	
 • MSEL & PSI 		
	Final Psychologist Assessment (teleconsultation)		60
	
 • VABS-III 		
		Video conferencing observation (FSC, NDBI-Fi)	30
Visit 15	Sixth Paediatrician visit (final visit)		30
	Paediatrician to share reports and discuss progress and further needs of child and family		
Post-interview will be conducted for eligible and chosen participants after intervention is completed, or after participant has transitioned to EIPIC.			45
End of study			

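### Non-inferiority is judged only on a per-protocol set defined by attendance after randomisation; no analysis of all randomised children is planned

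*Combined protocol and SAP*

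**What the plan says.** In Data Analysis Plan, Quantitative Outcomes, the plan states that "since the study is a non-inferiority study, statistical analysis will be carried out on a per-protocol basis" and that "Subjects with any major protocol deviation as defined above will be excluded from the final analysis". The decision rule in the next paragraph (lower 95% confidence limit for the MSEL difference above −5) names no other population.

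Protocol Deviation and Per-protocol Analysis defines a major deviation as completing less than 80% of the sessions allocated to the child's arm. It works this out for control only: "This means that a control arm participant must attend at least 8 out of 10 clinic-based sessions". It then adds: "For the remaining 2 sessions, participants can either be attending it through video-conferencing (due to the COVID-19 pandemic) or miss the appointment". No count is worked out for telerehab.

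Intervention: Standard Program, however, gives control "16 clinic-based intervention sessions of 60 min each, separated into 3 intervention blocks". Table 1 of the cost-effectiveness section, Annex 1 and Annex 2 also give 16. Annex 1 gives telerehab a fourth block that control does not have: "Video conference-based intervention (VCBI) x 6".

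Transfer to Early Intervention Programs says that "children in this study will continue to receive intervention for 10 weeks after EIPIC enrolment" and that "study participants who have been transferred to an EIPIC will still be assessed per protocol for Midterm Progress Reviews and Final Reviews and Assessments". Exit Review for Early Withdrawals offers an optional MSEL to children who leave after block 1, but the analysis plan gives that score no role.

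**The concern.** A filter on attendance after randomisation means that the groups compared may no longer be the groups that were randomised. If families who stop attending have children who progress differently, and if they are removed at different rates by arm, the per-protocol difference is biased. The bias can favour non-inferiority or work against it.

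A per-protocol set does belong in a non-inferiority trial, because it limits crossover that would pull the arms together. The difficulty is that here it stands alone. Without an all-randomised result beside it, a reader cannot tell whether the conclusion depends on who was excluded. The protocol sets this as an effectiveness trial run under routine operating conditions, and whether families keep attending is part of how a delivery mode performs.

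The one set that carries the conclusion is also not uniquely defined, so two analysts could build it differently.

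**Working it through.** **1. The plan's own sample size.** Inputs from Sample Size Calculation: margin 5, SD 15, assumed advantage 1.5, one-sided 5%, power 80%.

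n per arm = 2 × 15² × (1.645 + 0.842)² / (5 + 1.5)² = 65.9, so 66 per arm and 132 in total, as stated. Raising this to 200 allows for 1 − 132/200 = 34% loss. The total is not in dispute.

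**2. Does the filter treat the arms alike?** Cumulative sessions after blocks 1 to 4, from Annex 1:

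| Arm | Block 1 | Block 2 | Block 3 | Block 4 | 80% threshold |
|---|---|---|---|---|---|
| Control | 6 | 10 | 16 | 16 | 0.8 × 16 = 12.8 |
| Telerehab | 6 | 10 | 12 | 18 | 0.8 × 18 = 14.4 |

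- A child who attends everything through block 3, has no later sessions and returns for the final assessment has 16/16 in control (kept) but 12/18 = 67% in telerehab (excluded).
- In the other direction, the worked control rule counts clinic-based sessions. A fully attending control child with 4 of 16 sessions moved to video has 12/16 = 75%. On the 10-session reading, 3 moved leaves 7/10 = 70%. Either child could be excluded.
- Therapy continues for 10 weeks after EIPIC enrolment. Against the 40 to 60 weeks in Annex 2 that is 10/60 = 17% to 10/40 = 25% of the programme, which may limit how often transfer causes low attendance.

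**3. Is the set well defined?** Eight sessions are 80% of 10 but 8/16 = 50% of 16. The two counts cannot both be the control denominator.

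**4. Illustrative effect on the decision.** The documents give no attendance rates and no outcome gap, so these inputs are assumed: 100 randomised per arm, SD 15, excluded children gaining 5 to 10 points less in both arms, a true all-randomised difference of exactly −5, and a two-sided 95% interval.

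Bias = gap × (share excluded in telerehab − share excluded in control). With 30% and 20% excluded, SE = 15 × √(1/70 + 1/80) = 2.455; swapping the shares leaves it unchanged. False non-inferiority = Φ(bias/SE − 1.96).

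| Excluded, telerehab / control | Gap | Bias | False non-inferiority |
|---|---|---|---|
| 30% / 20% | 5 | +0.5 | 4.0% |
| 30% / 20% | 10 | +1.0 | 6.0% |
| 20% / 30% | 5 | −0.5 | 1.5% |
| 20% / 30% | 10 | −1.0 | 0.9% |
| equal | equal | 0 | 2.5% |

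A t-test simulation with 20,000 runs gave 3.8%, 6.2%, 1.6%, 0.9% and 2.4%. The all-randomised analysis in the same runs, with complete final scores, gave 2.0–2.4%.

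**5. How often would two analyses disagree, and what would requiring both cost?** Assumed: 75 per arm per-protocol, 90 or 100 per arm all-randomised, correlation √(75/90) or √(75/100), 95% interval rule.

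| Per-protocol difference | All-randomised difference | Power, per-protocol alone | Power, both required (90 / 100 per arm) |
|---|---|---|---|
| +1.5 | +1.5 | 75.6% | 73.6% / 73.9% |
| +1.5 | +0.5 | 75.6% | 66.2% / 67.9% |
| +1.5 | +2.5 | 75.6% | 75.4% / 75.4% |
| 0 | 0 | 53.2% | 49.8% / 49.8% |
| 0 | −1.0 | 53.2% | 40.4% / 41.4% |

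Disagreement = per-protocol power + all-randomised power − 2 × joint power. In the first row this is 0.756 + 0.828 − 2 × 0.736 = 11.2% with 90 per arm, and 0.756 + 0.865 − 2 × 0.739 = 14.3% with 100. Conflicting answers would therefore arise in about one trial in seven to nine even with no outcome gap.

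**The case against.** The strongest reply is that step 4 takes the all-randomised difference as the truth, so the all-randomised analysis looks sound by construction. Suppose instead that the target is the effect in adherent children: a true difference of −5 among them, none among the other 25% in each arm, and 100 per arm with complete data. The all-randomised difference is 0.75 × (−5) = −3.75 and SE = 15 × √(2/100) = 2.121. False non-inferiority is then Φ(1.25/2.121 − 1.96) = 8.5%, worse than the 4.0–6.0% above. This stands, and it is why the per-protocol analysis should stay. It supports reporting both analyses, not one alone.

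Other points have partial force:

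- The two block-3 children are not alike: the control child has finished therapy and the telerehab child has missed a third of it. Program Timeline also generally holds a child back until the planned sessions are done. That may make the case uncommon.
- A session by video may count as completed under the general 80% wording, and nothing suggests that children moved to video gain less. Step 4 does not represent that route.
- If losses reach the planned 34%, fewer final scores exist. With 66 per arm with outcomes and 60 per-protocol (assumed), power at +1.5 is 66% alone and 63% jointly, and disagreement is about 9%.
- The sample size uses one-sided 5%, while a two-sided 95% interval implies 2.5%. At a nominal 5% the error rates in step 4 would differ. That inconsistency is a separate matter.

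None of these supplies the missing analysis.

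**Conclusion.** The concern holds. The −5 decision rests solely on a set defined by attendance after randomisation, no all-randomised MSEL comparison is specified in the text available for review, and the only worked threshold contradicts the session count used everywhere else. These are findings of fact from the text.

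Bias is possible but not shown. Its direction and size depend on exclusion rates and outcome gaps that the documents do not give. Under the stated assumptions it is 0.5 to 1.0 points either way, and zero when exclusions and gaps are equal. The plan should be changed, but choosing a per-protocol analysis is not itself an error.

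**What to change.** - Keep the per-protocol analysis. Add a baseline-adjusted analysis of all randomised children in their assigned arm, using every final MSEL, including those of children below the attendance threshold or moved to EIPIC.
- Apply the same −5 margin and state in advance how disagreement will be read. Requiring both lower limits to exceed −5 is one option; treating the all-randomised result as supportive is another.
- Do not use an exit-review MSEL as a final score without allowing for its earlier timing. It could enter a missing-data model, with a sensitivity analysis.
- Reconcile the control session denominator across Protocol Deviation and Per-protocol Analysis, Intervention: Standard Program, Table 1, Annex 1 and Annex 2. State the telerehab threshold and how video sessions count in control.
- Report exclusions by arm and reason.

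The cost is SAP wording and programming, with no new visits. Some final scores will be missing, because the exit review is optional and offered only after block 1, and children who do not complete a phase may not reach the final assessment. Scores after transfer may also reflect outside treatment, which the Time Horizon section describes as varying considerably. A supportive analysis costs no power. Requiring both limits costs about 2 points of power at +1.5 with no outcome gap, and about 8 to 9 points if the all-randomised difference is 1 point lower.
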